Protocol for non-interventional studies based on existing data

Document Number:	<document number>
BI Study Number:	1245-0198
BI Investigational Product(s):	NA
Title:	Description of Treatment and Population Characteristics of Type 2 Diabetic Patients in Germany receiving Empagliflozin: A retrospective Real-World Evidence (RWE) study based on German registries DPV & DIVE
Protocol version identifier:	1.0
Date of last version of protocol:	16 August 2019
PASS:	No
EU PAS register number:	NA
Active substance:	Empagliflozin
Medicinal product:	Jardiance®, Synjardy®
Product reference:	NA
Procedure number:	NA
Joint PASS:	—
Research question and objectives:	
Description of the real-life treatment of adult patients with type-2 diabetes mellitus (T2DM) receiving Empagliflozin, comparing the characteristics of patients starting Empagliflozin in three time intervals:
 
 - The first analysis will include the patients receiving Empagliflozin before the EMPA-REG-OUTCOME study was published (time until mid-Sept. 2015; “Cohort 1”). - The second analysis will include patients receiving Empagliflozin starting from the EMPA-REG-OUTCOME study being published until CV Label Change (time from mid-Sept. 2015-mid-Jan. 2017; “Cohort 2”). - The third analysis will include all patients receiving Empagliflozin starting from mid-Jan. 2017 until last available data cut (“Cohort 3”).
Country of study:	Germany

Author:				
Marketing authorisation holder(s):				
MAH contact person:				
In case of PASS, add: <EU-QPPV:>	NA			
In case of PASS, add: <Signature of EU-QPPV:>	NA			
Date:	16 August 2019			
Page 1 of 32				
Proprietary confidential information © 2020 Boehringer Ingelheim International GmbH or one or more of its affiliated companies. All rights reserved. This document may not - in full or in part - be passed on, reproduced, published or otherwise used without prior written permission				

2. LIST OF ABBREVIATIONS

ACE-i	Angiotensin-converting enzyme inhibitor
AD	Anti-diabetic Drug
aDCSI	adapted Diabetes Complications Severity Index
ADR	Adverse Drug Reaction
AE	Adverse Event
AESI	Adverse Event of Special Interest
ARB	Angiotensin receptor blocker
ASA	Acetylsalicylic acid (Aspirin)
ASCVD	Atherosclerotic cardiovascular disease
ATC	Anatomical Therapeutic Chemical / Defined Daily Dose Classification
AWMF	Arbeitsgemeinschaft der Wissenschaftlichen Medizinischen Fachgesellschaften e.V.
BÄK	Bundesärztekammer
Ba-Wue.	Baden-Wuerttemberg
BB	Beta blocking agents
BI	Boehringer Ingelheim
CAD	Coronary artery disease
CCB	Calcium-channel blockers
CCI	Charlson Comorbidity Index
CI	Confidence Interval
CRO	Clinical Research Organization
CSME	Clinically significant macular edema/degeneration
CV	Cardiovascular
CVD	Cardiovascular disease
DDD	Defined Daily Dose
DMP	Diseases Management Program
DPP4-i	Dipeptidylpeptidase IV inhibitors
DRG	Diagnosis Related Group
EBM	Einheitlicher Bewertungsmaßstab
EU-QPPV	European Union Qualified Person for Pharmacovigilance
FGS	Fachgruppenschlüssel
GPP	Good Pharmacoepidemiology practices
HMG-CoA	3-hydroxy-3-methyl-glutaryl-coenzyme A
Hosp.	Hospitalization
IC	Informed Consent
ICD	International Statistical Classification of Diseases and Related Health Problems
ICH-GCP	International Council for Harmonization of Technical Requirements for Pharmaceuticals for Human Use
IEC	Independent Ethics Committee
IHD	Ischemic heart disease
IPAM	Institut für Pharmakoökonomie und Arzneimittellogistik
ISPE	International Society for Pharmacoepidemiology
ISPOR	International Society for Pharmacoeconomics and Outcomes Research

KBV	Kassenärztliche Bundesvereinigung
KM	Kaplan-Meier
LOCF	Last observation carried forward
MAH	Marketing authorization holder
MI	Myocardial infarction
MRA	Mineralocorticoid receptor antagonists / Aldosterone antagonists
NIS	Non-interventional study
NOAC	New Oral Anticoagulant
NYHA	New York Heart Association
OAC	Oral anticoagulation
OPS	"Operationsschlüssel"
PAD	Peripheral artery disease
PAI	Platelet aggregation inhibitor
PASS	post-authorization safety study
PhRMA	Pharmaceutical Research and Manufacturers Association
PVD	Peripheral vascular disease
PY	Patient year
PZN	"Pharmazentralnummer"
RAAS-i	Renin-angiotensin-aldosterone system inhibitor
SU	Sulfonylureas
T2DM	Type-2 Diabetes Mellitus
TIA	Transient ischemic attack
VKA	Vitamin K antagonist

4. ABSTRACT

Name of company: Boehringer Ingelheim			
Name of finished medicinal product: Jardiance®, Synjardy®			
Name of active ingredient: Empagliflozin			
Protocol date: 16 August 2019	Study number: 1245-0198	Version/Revision: 1.0	Version/Revision date:
Title of study:	Description of Treatment and Population Characteristics of Type 2 Diabetic Patients in Germany receiving Empagliflozin: A retrospective Real-World Evidence (RWE) study based on German registries DPV & DIVE		

Rationale and background:	
In the following years, new data for empagliflozin in type 2 diabetes (T2D) from clinical studies and PMO data will be limited. To gain a comprehensive picture of a drug's (long-term) effectiveness, the medical community, payers and health politicians demand real-world evidence (RWE).
 
In general, collaboration with a registry allows a continuous scientific exchange (e.g. scientific discussions and publications). RWE is also part of the basis for generating payer partnerships, e.g. managed-care projects. Furthermore, the data can be used for value communication for payers and medical communities (e.g. via digital channels). In addition, AMNOG price negotiations could be supported by such data.
 
Therefore, we plan to perform a retrospective, non-interventional study on the real-life treatment and treatment-associated outcomes of German T2D patients receiving Empagliflozin. We will set up this study based on data from the two largest German registries (Diabetes-Patienten-Verlaufs-dokumentation (DPV) & Diabetes Versorgungs-Evaluation (DIVE)) covering currently around 500,000 adult T2D patients in Germany. The number of SGLT2i patients in Germany is steadily increasing.
 
In this study, only Empagliflozin patients will be analyzed. They will be divided in three consecutive cohorts to assess potential differences over time.

Research question and objectives:	
Description of the real-life treatment of adult patients with T2DM receiving empagliflozin, comparing the characteristics of patients starting empagliflozin in three time intervals:
 
 - The first analysis will include the patients receiving Empagliflozin before the EMPA-REG-OUTCOME study was published (time until mid-Sept. 2015; "Cohort 1"). - The second analysis will include patients receiving Empagliflozin starting from the EMPA-REG-OUTCOME study being published until CV Label Change (time from mid-Sept. 2015-mid-Jan. 2017; "Cohort 2"). - The third analysis will include all patients receiving Empagliflozin starting from mid-Jan. 2017 until last available data cut ("Cohort 3").
Study design:	
Retrospective non-interventional cross-sectional study using real-world data from German patient registries. Data will be provided by the largest German T2D patient registries DPV& DIVE covering more than 500,000 patients.

Population:	
Inclusion criteria:
 
 • Adult patients with at least two outpatient T2DM diagnoses (ICD E11.-) in two different quarters and/or at least one inpatient T2DM diagnosis (ICD E11.-) – AND – • At least one prescription of an empagliflozin-containing antidiabetic drug: Jardiance® (Empagliflozin, ATC A10BK03, former

	A10BX12) or Synjardy® (Empagliflozin/Metformin, ATC A10BD20)
--	---

Exclusion criteria

- Any diagnosis of T1DM.

Variables:	
For all three cohorts receiving empagliflozin, the baseline values of the following variables will be assessed:
 
 • Age (<65; 65 – <75; 75 – 80 , >80) • Gender • Weight [kg] • Height [cm] • HbA1c [% or mmol/ mol], FPG (available in subgroup only) • Previous occurrence of 
 ◦ Typical CV comorbidities: 
 ▪ MI ▪ Stroke ▪ CAD ▪ PAD ▪ CHF (form (HFrEF/ HFpEF) ◦ Other typical diabetes complications 
 ▪ Neuropathy ▪ Nephropathy / Renal function (eGFR, micro-/ macroalbuminuria) ▪ Diabetic foot syndrome ▪ Retinopathy (background and proliferative) • Antidiabetic and cardiovascular co-medication (lipid-lowering agents, RAAS blockers, other antihypertensives, beta blockers, diuretics, antiplatelets and anticoagulants) • Duration of diabetes (time since diagnosis) • Previous glucose-lowering treatment • Dosage of empagliflozin (10mg vs 25mg) (available in subgroup only) • Participation in Disease Management Programme (DMP) Type 2 Diabetes (from DPV registry) • Hospitalizations (from DPV registry)
Data sources:	
Data will be provided by the largest German T2D patient registries DPV& DIVE covering more than 500,000 patients.
 
The aim of the DPV initiative is to improve treatment outcomes in individuals with diabetes through standardized documentation and objective comparison of quality indicators as well as through multi-centre outcome research. Up to date, there are more than 400 centres participating in the initiative predominantly from Germany and from Austria.
 
DIVE is a national initiative for quality management of diabetes care. The aim is to transfer the already existing initiatives and software systems which collect patient-related data to a national diabetes registry. The DIVE registry is one of the biggest, most updated diabetes registries in Germany and part of the current development of a national diabetes registry. It is part of the first and second registry conference held by German Federal Ministry of Health (BMG) and Robert-Koch Institute (RKI).

Study size:	There will be about 7,900 patients on Empagliflozin included in the analysis.
Data analysis:	
Variables will be assessed in half-yearly periods after index date (date of first prescription of empagliflozin), for total study population and separated by study cohort.
 
Anonymized data from the DIVE and the DPV registries will be combined; nonparametric descriptive analyses will be used. Group comparison will be based on Wilcoxon rank sum test (continuous variables) and X²-test for binary/categorial values. Analysis will be implemented using SAS 9.4. Complete case analysis will be used.
 
Analysis will be done by an experienced biostatistician with detailed knowledge of the DIVE and the DPV registries. A second independent programmer will check the generated SAS code for inconsistencies. The medical team (
 
will evaluate the results from a clinical background to ensure plausibility.
 
Quality assurance and control will be the responsibility of the medical team (

Milestones:	
 • Project kick-off: 09 November 2018 • Draft of study protocol: 5 July 2019 • Final study protocol & approval by: 31 August 2019 • Start of data access/data validation: 01 September 2019 • End of data analysis by: 31 October 2019 • Final report of study results by: 31 December 2019 • Finalization of publication draft by: 31 December 2019

5. AMENDMENTS AND UPDATES

None.

6. MILESTONES

Milestone	Planned Date
-----------	--------------

7. RATIONALE AND BACKGROUND

In the following years, new data for empagliflozin in type 2 diabetes (T2D) from clinical studies and PMO data will be limited. To gain a comprehensive picture of a drug's (long-term) effectiveness, the medical community, payers and health politicians demand real-world evidence (RWE).

In general, collaboration with a registry allows a continuous scientific exchange (e.g. scientific discussions and publications). RWE is also part of the basis for generating payer partnerships, e.g. managed-care projects. Furthermore, the data can be used for value communication for payers and medical communities (e.g. via digital channels). In addition, AMNOG price negotiations could be supported by such data.

Therefore, we plan to perform a retrospective, non-interventional study on the real-life treatment and treatment-associated outcomes of German T2D patients receiving Empagliflozin. We will set up this study based on data from the two largest German registries (Diabetes-Patienten-Verlaufsdocumentation (DPV) & Diabetes Versorgungs-Evaluation (DIVE)) covering currently around 500,000 adult T2D patients in Germany. The number of SGLT2i patients in Germany is steadily increasing.

In this study, only Empagliflozin patients will be analyzed. They will be divided in three consecutive cohorts to assess potential differences over time.

8. RESEARCH QUESTION AND OBJECTIVES

Description of the real-life treatment of adult patients with T2DM receiving empagliflozin, comparing the characteristics of patients starting Empagliflozin in three time intervals:

- The first analysis will include the patients receiving Empagliflozin before the EMPA-REG-OUTCOME study was published (time until mid-Sept. 2015; "Cohort 1").
- The second analysis will include patients receiving Empagliflozin starting from the EMPA-REG-OUTCOME study being published until CV Label Change (time from mid-Sept. 2015-mid-Jan. 2017; "Cohort 2").
- The third analysis will include all patients receiving Empagliflozin starting from mid-Jan. 2017 ("Cohort 3") until last available data cut.

9. RESEARCH METHODS

9.1 STUDY DESIGN

Retrospective non-interventional cross-sectional study using real-world data from German patient registries. Data will be provided by the largest German T2D patient registries DPV& DIVE covering more than 500,000 patients. An anonymized dataset will be delivered by DIVE and DPV, respectively. The two datasets will then be combined.

9.2 SETTING AND INCLUSION/EXCLUSION CRITERIA

Description of the real-life treatment of adult patients with T2DM receiving empagliflozin, comparing the characteristics of patients starting empagliflozin in three time intervals:

- The first analysis will include the patients receiving Empagliflozin before the EMPA-REG-OUTCOME study was published (time until mid-Sept. 2015; “Cohort 1”).
- The second analysis will include patients receiving Empagliflozin starting from the EMPA-REG-OUTCOME study being published until CV Label Change (time from mid-Sept. 2015-mid-Jan. 2017; “Cohort 2”).
- The third analysis will include all patients receiving Empagliflozin starting from mid-Jan. 2017 until last available data cut (“Cohort 3”).

Inclusion criteria:

- At least two outpatient T2DM diagnoses (ICD E11.-) in two different quarters and/or at least one inpatient T2DM diagnosis (ICD E11.-)
- At least one prescription of an empagliflozin-containing antidiabetic drug: Jardiance® (Empagliflozin, ATC A10BK03, former A10BX12) or Synjardy® (Empagliflozin/ Metformin, ATC A10BD20)

Exclusion criteria

- Any diagnosis of T1DM

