9.5 STUDY SIZE

There will be about 7,900 patients on Empagliflozin included in the analysis.

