9.7 DATA ANALYSIS

9.7.1 Main analysis

Variables will be assessed in half-yearly periods after index date (date of first prescription of empagliflozin), for total study population and separated by study cohort.

Anonymized data from the DIVE and the DPV registries will be combined; nonparametric descriptive analyses will be used. Group comparison will be based on Wilcoxon rank sum test (continuous variables) and X²-test for binary/categorial values. Analysis will be implemented using SAS 9.4. Complete case analysis will be used.

Analysis will be done by an experienced biostatistician with detailed knowledge of the DIVE and the DPV registries. A second independent programmer will check the generated SAS code for inconsistencies. The medical team (

will evaluate the results from a clinical background to ensure plausibility.

Quality assurance and control will be the responsibility of the medical team (

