3.3 Does the protocol specify measures of occurrence? (e.g. incidence rate, absolute risk)				9.7

¹ Date from which information on the first study is first recorded in the study dataset or, in the case of secondary use of data, the date from which data extraction starts.

² Date from which the analytical dataset is completely available.

Section 3: Study design	Yes	No	N/A	Section Number
3.4 Does the protocol specify measure(s) of association? (e.g. relative risk, odds ratio, excess risk, incidence rate ratio, hazard ratio, number needed to harm (NNH) per year)				9.7
3.5 Does the protocol describe the approach for the collection and reporting of adverse events/adverse reactions? (e.g. adverse events that will not be collected in case of primary data collection)				(11)

Comments:

--

Section 4: Source and study populations	Yes	No	N/A	Section Number
4.1 Is the source population described?				9.4
4.2 Is the planned study population defined in terms of:				9.2
4.2.1 Study time period?				9.2
4.2.2 Age and sex?				9.2
4.2.3 Country of origin?				9.2
4.2.4 Disease/indication?				9.2
4.2.5 Duration of follow-up?				9.2
4.3 Does the protocol define how the study population will be sampled from the source population? (e.g. event or inclusion/exclusion criteria)				9.2

Comments:

--

Section 5: Exposure definition and measurement	Yes	No	N/A	Section Number

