5.1 Does the protocol describe how the study exposure is defined and measured? (e.g. operational details for defining and categorizing exposure, measurement of dose and duration of drug exposure)				-
5.2 Does the protocol address the validity of the exposure measurement? (e.g. precision, accuracy, use of validation sub-study)				-
5.3 Is exposure classified according to time windows? (e.g. current user, former user, non-use)				-
5.4 Is exposure classified based on biological mechanism of action and taking into account the pharmacokinetics and pharmacodynamics of the drug?				-

Comments:

As this is a cross-sectional study, there will be no follow-up period and thus no exposure measurement. A patient will be included after the first available record of drug use.

Section 6: Outcome definition and measurement	Yes	No	N/A	Section Number
6.1 Does the protocol specify the primary and secondary (if applicable) outcome(s) to be investigated?				9.3
6.2 Does the protocol describe how the outcomes are defined and measured?				9.3
6.3 Does the protocol address the validity of outcome measurement? (e.g. precision, accuracy, sensitivity, specificity, positive predictive value, prospective or retrospective ascertainment, use of validation sub-study)				9.8
6.4 Does the protocol describe specific endpoints relevant for Health Technology Assessment? (e.g. HrQoL, QALYs, DALYs, health care services utilization, burden of disease, disease management)				9.3

Comments:

--

Section 7: Bias	Yes	No	N/A	Section Number
7.1 Does the protocol describe how confounding will be addressed in the study?				

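### Does the missing time window on the E11 diagnosis rule leave the analysed population undefined?

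*Combined protocol and SAP*

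**What the plan says.** Section 9.2 sets the diagnosis criterion as "At least two outpatient T2DM diagnoses (ICD E11.-) in two different quarters and/or at least one inpatient T2DM diagnosis (ICD E11". The abstract repeats it and adds that patients are adults: "Adult patients with at least two outpatient T2DM diagnoses (ICD E11.-) in two different quarters and/or at least one inpatient T2DM diagnosis (ICD E11". Both add at least one empagliflozin prescription. The sole exclusion is "Any diagnosis of T1DM". None of these criteria is placed in time relative to the first prescription.

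The index date is defined only in 9.7.1, and there it times the variables, not eligibility: "Variables will be assessed in half-yearly periods after index date (date of first prescription of empagliflozin"). Section 9.10 includes all patients with T2DM in the two registries who receive empagliflozin, again without timing. Cohort 3 is open-ended: "The third analysis will include all patients receiving Empagliflozin starting from mid-Jan. 2017 until last available data cut". Section 9.5 gives the expected size: "There will be about 7,900 patients on Empagliflozin included in the analysis".

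Two entries in Annex 2 touch on the point. The item "4.2.5 Duration of follow-up" is ticked Yes with a pointer to 9.2. The comment under Section 5 of the checklist reads: "As this is a cross-sectional study, there will be no follow-up period and thus no exposure measurement".

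**The concern.** Where the index date falls part-way through a patient's record, an eligibility rule normally says on which side of it the qualifying records may lie. Here it does not, and the hints conflict. Half-yearly assessment after index implies that later records are in the extract. The cross-sectional label in 9.1, the abstract's reference to baseline values and the checklist's denial of any follow-up suggest data up to index only.

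Two readings are therefore conceivable:

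- **A:** any E11 record up to the data cut counts.
- **B:** only records up to the index date or index quarter count.

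If analysts could choose freely between them, the second programmer's code check (9.8) would have no written rule to test against, and the choice could be made after the data were seen. Reading A also treats the cohorts slightly differently. An outpatient who starts in the quarter of the data cut and has no earlier E11 quarter has no later quarter in which to qualify. Only Cohort 3 runs up to the cut, and the cohorts are what the study compares.

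**Working it through.** **1. Which reading the text supports.**

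| Place | What it contributes |
|---|---|
| 9.2 and abstract, inclusion | No time limit: favours A |
| 9.2, exclusion | Any T1DM diagnosis, no limit: favours A |
| 9.10 | All T2DM patients receiving empagliflozin: favours A |
| 9.7.1 | Post-index records are used: compatible with A |
| 9.1 and abstract (cross-sectional, baseline values) | Describes design and variables: silent on eligibility |
| Annex 2, Section 5 comment | No follow-up: leans to B, but explains why exposure items are not applicable |
| Annex 2, item 4.2.5 | Credits 9.2 with a follow-up duration; 9.2 has only calendar intervals: settles nothing |

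A programmer who applies 9.2 as written uses no window, which is A. Reading B needs an added restriction whose only textual support is a comment on another topic.

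**2. Who differs between A and B.** More than one kind of patient does:

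- outpatients with no E11 quarter before the index quarter but one after it;
- outpatients with a single earlier E11 quarter, none in the index quarter and one later;
- patients whose only inpatient E11 record comes after index and who have not met the outpatient route by then;
- patients whose only T1DM code is after index, if the exclusion takes the same window (excluded under A, kept under B).

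**3. Size.** The documents give no data cut, no outpatient share and no record history, and the figure of about 7,900 comes without inputs, so there is nothing to reproduce. What follows is illustrative and covers only the first kind of patient.

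Assumptions: 80% of starters are outpatient-only; 5% to 20% of these have no earlier E11 quarter; 10% to 30% of that group are never recorded again and the rest return in the next quarter; starts are uniform from 15 January 2017.

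- Group share g = 0.80 × 0.05 = 0.04 to 0.80 × 0.20 = 0.16 of starters.
- Never recorded again: r = 0.10 to 0.30.
- In under A but not B, Cohorts 1 and 2: g(1 − r) = 0.04 × 0.7 = 2.8% to 0.16 × 0.9 = 14.4%.
- Share of Cohort 3 entry days in the cut quarter: q = 62/959 = 6.5% (assumed cut 1 September 2019), 91/897 = 10.1% (30 June 2019) or 92/716 = 12.8% (31 December 2018).
- In under A but not B, Cohort 3: g(1 − r)(1 − q) = 2.8% × 0.872 = 2.4% to 14.4% × 0.935 = 13.5%.
- Loss under A peculiar to Cohort 3: g(1 − r)q = 2.8% × 6.5% = 0.18% to 14.4% × 12.8% = 1.85%.

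These percentages should not be turned into patient counts from 7,900. That figure is for patients included in the analysis, after eligibility, while the shares refer to all starters.

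**4. Effect on a Cohort 3 percentage under A.** At the upper end, the share of starters kept is 1 − gr − g(1 − r)q = 1 − 0.016 − 0.0185 = 0.9655, if all other starters qualify. Losing 0.0185 shifts a prevalence by 0.0185/0.9655 = 0.019 times the gap between the lost patients and the cohort as a whole. No plausible gap makes that important in a descriptive comparison.

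**The case for a change.** The best case for acting is that the gap is real, no passage closes it, and one sentence in 9.2 and the abstract would. Silence is not the same as a stated rule. A programmer who stops at index in a study labelled cross-sectional, whose checklist denies any follow-up, could claim to be following the protocol. The assumed gap of 2.8% to 14.4% between the readings is not negligible, it covers only one of the affected groups, and the data already exist.

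What stands is that the window is unstated and that the documents disagree about the use of post-index data. That disagreement concerns when the variables are measured, not who is eligible.

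The rest carries less weight. The 2.8% to 14.4% measures the distance from the literal rule to a restriction that the protocol does not contain, and every share in it is assumed. Stating the window would not make the study size reproducible, because 9.5 gives no inputs and Annex 2 marks sample size as not applicable. The possibility of a choice after seeing the data applies to any unwritten detail and is not evidence of a problem here. Exclusion counts by cohort, or a sensitivity analysis ending Cohort 3 early, would address an assumed loss of at most 1.9% of one cohort.

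**Conclusion.** No change to the plan is called for. The missing window is a detail that analysts can fill sensibly by applying the criteria as written, to all available records and in the same way in all three cohorts. Either window would be defensible: the rule serves to confirm a chronic disease, and the study is descriptive with no prior hypothesis (Annex 2, item 2.1.5). No bias is shown, and the documents do not allow the effect on the population or on any outcome to be sized. Under the literal reading, the one asymmetry between cohorts comes to 0.2% to 1.9% of Cohort 3, on the assumptions of uniform starts, return in the next quarter and the shares listed above. Rising use or later return would raise it; counting a historical diagnosis date as an earlier quarter would lower it. The checklist tick for follow-up duration is a clerical slip with no bearing on eligibility.
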